### **Dose Escalation**

For all MTDs (initial, subsequent and target doses), dose escalation will estimate the MTD. The estimated MTD is defined as the maximum dose at which fewer than

one-third of subjects experience a dose limiting toxicity (DLT) (minimum of 6 evaluable subjects for the target dose MTD; see Section 3.4 for definition of evaluable).

Dose Escalation will be conducted in two stages. In the single subject cohorts, single subjects will be enrolled at dose levels anticipated to be lower than those at which adverse events will be observed. Once higher dose levels are open for enrollment or when drug related safety or efficacy signals are observed (see below), the 3+3 design will be triggered.

Subjects who complete the DLT period (see Section 6.2.1.4) may proceed to a higher dose level for the following treatment cycle if no DLT has been reported for either this subject or any other subject in this dose cohort after completion of the DLT period, and once the next higher dose cohort is open for enrollment, after consultation with the sponsor (see Section 7.2.2 for details on assessments applicable in case of intra-subject dose escalation). DLTs experienced by subjects who proceeded to a higher dose as described above will not be considered for 3+3 decisions. However, the Dose Level Review Team (DLRT) may take this information into account to inform dose escalation recommendations.

Should the initial dose be limited by adverse events related to first dose effects (eg, cytokine release syndrome), dose steps will be implemented. The MTD for the target dose will be estimated after giving the initial dose (and subsequent step doses if applicable) at their respective MTD(s). This means that the cohort for which a dose step will be implemented will start treatment for the first days at the first MTD assessed in the prior cohort. After this run in phase, there may be a dose increase to the next higher dose as per the dosing schedule shown in Table 4 of the protocol. If a 960 µg/day target dose is not the MTD, further dose escalation to a higher target dose up to 1.6 mg is allowed to reach MTD according to the rules described above. If this treatment schedule is tolerated, following dose cohorts will continue to receive the run in (initial) dose at the initial/1st MTD to assess the 2nd MTD. The target dose will be increased until a second MTD is reached. This 2nd MTD is the highest subsequent dose (day of dose step until end of cycle) with <33% of subjects experiencing a DLT. Each MTD will be estimated following 3+3 decision rules (Table 5). If additional dose steps are implemented, an MTD for each step will be determined using the same algorithm. To optimize the dose step schedule, additional intermediate steps below established MTD levels can be introduced based on DLRM recommendation.

The 1st run-in dose **and each** subsequent dose step should be administered for **1 to 5 days**. The treatment interval for all dose steps will be recommended by the DLRT based on the available safety, tolerability, PK, and PD data.

Starting with cohort 6, if there is an infusion free period of >24 hours between cycles, one or more dose steps in each cycle are mandatory for all subjects. Administration of a prophylactic steroid dose (8 mg IV dexamethasone) within 1 hour prior to the dose step for prevention of cytokine release is mandatory (see also Section 6.5). The additional assessments described in the schedule of assessments for dose steps ([Table 14](#)) apply. The DLRT may also recommend to implement additional dose steps in a cycle if this was considered appropriate and necessary to allow further dose escalation. The additional dose step(s) would be performed the same way as described above. In this case, an additional MTD would be estimated for the dose to be administered after the last dose step.

### Single Subject Cohorts

In the initial dose escalation cohorts, only a single subject will be enrolled to a cohort because the dose level is not anticipated to be clinically active. AMG 330 will initially be administered at escalating doses in a 2 weeks on / 1-4 weeks off schedule. This schedule may be modified by DLRT recommendation (see Section [6.2.1.1](#) for details).

The 3+3 design will be triggered if at least 1 subject experiences any of the following drug related safety or efficacy signals (whichever is earlier):

- Common Terminology Criteria for Adverse Events (CTCAE) grade  $\geq 2$  adverse event other than thrombocytopenia, anemia, or neutropenia
- DLT
- Objective response.

### **Multiple Subject Cohorts (3+3 Dose Level Decision Rules)**

Based on nonclinical models, the dose for cohort 4 is predicted to be potentially efficacious. It is anticipated that up to 8 additional cohorts will be enrolled using a standard 3+3 design. Each cohort will enroll up to 6 evaluable subjects. There will be at least a 6-day (144-hour) interval between the start of treatment of the first and second subject in each cohort. On day 6 of this interval, the site investigator will evaluate all available safety and laboratory data for the treated subject and will send written confirmation on occurrence / non-occurrence of a DLT to the sponsor. The sponsor will only be able to open enrollment for the next subjects in the cohort after receipt of this confirmation. If deemed necessary, the 6-day interval may be extended until sufficient data are available to allow an assessment of the feasibility of treatment start of the next subject. The same guidance applies in case of intra-subject dose escalation, if applicable.

Following this, no more than 3 subjects should be enrolled into a cohort in two weeks.

Dose escalation decisions will be made in accordance with a standard 3+3 design using the rules noted in [Table 5](#).

- If no DLT is observed within the DLT window (see Section [6.2.1.4](#)) in the initial 3 subjects of a cohort, then dose escalation to the next higher dose level cohort will occur.
- If 1 DLT is observed within the DLT window in the initial 3 subjects of a cohort, then the cohort will be expanded to 6 subjects when 2 non-DLT subjects have reached the target dose. If no further DLT(s) are observed in the 6 subjects, then dose escalation to the next higher dose level cohort will occur. If  $\geq 2$  subjects experience a DLT in a cohort, then enrollment into this cohort will be stopped.
- See Section [3.4](#) for replacement of subjects

Dose escalation will occur at the planned dose levels until the MTD is determined or until the highest dose level is tested. The MTD is defined as the highest dose level with an observed incidence of DLT in  $< 33\%$  of subjects enrolled in a cohort dose level. At least 6 subjects will be treated at the MTD or highest tested dose.

**Table 5. 3+3 Dose Level Decision Rules**

# Subjects a	#Subjects with DLT	Decision
3	1	Enroll 3 additional subjects at same dose level
3	0	Escalate b
3	≥ 2	De-escalate c
6	1	Escalate b
6	≥ 2	De-escalate c

[figure not shown]
a Subjects who are not DLT-evaluable (see Section 3.4) are excluded from the count of subjects

b If final dose level has been reached, accrual will be suspended.

c If 6 subjects already entered at next lower dose level, the estimated MTD has been established.

### **3.1.2 Design of Group 2: MRD+ AML**

The dose-escalation cohorts will estimate the safety, tolerability, PK, and PD of AMG 330 in subjects with MRD+ AML. The following dose escalation cohorts will be evaluated:

Selected

target dose levels, with the exception of the maximal tested dose, that have been deemed safe in subjects with R/R AML (Group 1) could be skipped in Group 2 dose escalation cohorts based on available safety, PK, and PD data if recommended by the DLRT. Administration of 8 mg IV dexamethasone within 1 hour prior to the dose step for prevention of cytokine release is mandatory. Up to 36 subjects with MRD+ AML will be enrolled in the phase 1a dose escalation cohorts; each dose escalation cohort will include a minimum of 3 and a maximum of 9 evaluable subjects.

### 3.1.3 Design of Group 3: MDS

The dose-escalation cohorts will estimate the MTD, safety, tolerability, PK, and PD of AMG 330 in subjects with MDS. The following dose escalation cohorts will be evaluated:

[REDACTED]

Selected

**target dose levels, with the exception of the maximal tested dose, that have been deemed safe in subjects with R/R AML (Group 1) could be skipped in Group 3 dose escalation cohorts based on available safety, PK, and PD data if recommended by the DLRT.** Administration of 8 mg IV dexamethasone within 1 hour prior to the dose step for prevention of cytokine release is mandatory. Up to 36 subjects with MDS will be enrolled in the phase 1a dose escalation cohorts; each dose escalation cohort will enroll a minimum of 3 and a maximum of 9 evaluable subjects.

### 3.1.4 Dose Escalation Rules for Groups 2 and 3

For both Group 2 and Group 3, a minimum of 3-4 subjects will be enrolled initially into each cohort and additional subjects up to a maximum of 9 evaluable subjects will be added at the Sponsor's discretion. After all subjects in each dose escalation cohort have either completed the DLT evaluation period or had a DLT, the DLRT will meet to determine whether it is appropriate to escalate or de-escalate the dose, or whether to stop the study for safety concerns. The DLRT will evaluate all available safety, laboratory, PK, and PD data to guide their dose-finding recommendations. **Based on DLRT recommendation, selected target dose levels, with the exception of the maximal tested dose, may be skipped in Groups 2 and 3 dose escalation cohorts if these dose levels have been evaluated in subjects with R/R AML (Group 1) and deemed safe.** [Appendix H](#) shows the mTPI-2 escalation/de-escalation guideline with a

target toxicity probability of 0.25 and an acceptable toxicity probability interval of 0.20 to 0.30. A dose level will be considered unsafe, with no additional subjects enrolled at that dose level, if it has an estimated  $> 95\%$  probability of exceeding the target DLT rate  $p_T$  (ie,  $P [DLT > p_T | \text{data}] > 95\%$ ) with at least 3 subjects treated and evaluated at that dose level. Dose exploration will continue until the current recommended dose cohort reaches at least 6 evaluable subjects or until the highest protocol-defined dose has been evaluated.

The MTD will be defined as the dose for which the estimate of the toxicity rate from an isotonic regression (Ji et al, 2010) is closest to the target toxicity rate. The DLRT will recommend the RP2D using the totality of the clinical and laboratory data from the dose exploration stage.

### **3.1.5 Expansion Cohorts for Groups 1, 2 and 3**

At completion of the dose escalation cohorts, additional subjects will be enrolled in a dose expansion cohort to gain further clinical experience, safety and efficacy data in subjects with AMG 330. The dose to be evaluated will be at or below the highest tested dose or the MTD estimated in the dose escalation cohorts. If there are at least 1 subject having response in the first 10 subjects enrolled in the expansion cohort, additional (up to 20) subjects may be enrolled after evaluating safety, tolerability, and anti-leukemia activity of AMG 330 using all available cumulative data.

A final estimate of the MTD and RP2D will be evaluated and confirmed utilizing all DLT -evaluable subjects from the dose escalation and the dose expansion cohorts. For definition of DLT-evaluable, see Section 3.4.

The overall study design is described by a study schema at the end of the protocol synopsis section.

The study endpoints are defined in Section 10.1.1.

### **3.1.6 Design of Alternative Cytokine Release Syndrome (CRS) Prophylaxis Groups**

An alternative approach for the prophylaxis of CRS will be evaluated in two groups of subjects with R/R AML.

In Group 4, [REDACTED] will be evaluated for CRS prophylaxis as alternatives to currently used 8 mg dexamethasone premedication administered 1 hour before AMG 330 start or step dose. Group 5 will receive an optimized dose step

approach with either [REDACTED], depending on which premedication yields optimal results in Group 4.

### 3.1.6.1 Group 4 Design

Group 4 will consist of two arms of R/R AML subjects. In treatment cycle 1, Arm 1 will receive prophylaxis with [REDACTED] and Arm 2 will receive prophylaxis with [REDACTED]. Subjects in each arm will receive a single agent for pretreatment, and dexamethasone will not be used for CRS prophylaxis. If CRS occurs during treatment with AMG 330, the management guidelines in [Table 7](#) should be followed.

#### 3.1.6.1.1 Group 4 Design – Cycle 1 ([REDACTED])

**Arm 1** ([REDACTED]): AMG 330 will be administered on day [REDACTED] at [REDACTED] µg/day for [REDACTED] days, [REDACTED] µg/day for [REDACTED] days and [REDACTED] µg/day for [REDACTED] days for a total cycle of [REDACTED] days with a [REDACTED]-day DLT period. [REDACTED]  
[REDACTED].

**Arm 2** ([REDACTED]): AMG 330 will be administered on day [REDACTED] at [REDACTED] µg/day for [REDACTED] days, [REDACTED] µg/day for [REDACTED] days and [REDACTED] µg/day for [REDACTED] days for a total cycle of [REDACTED] days. [REDACTED]  
[REDACTED].

Each premedication group will enroll a total of 6 evaluable subjects. Within each Arm, 3 subjects will initially be enrolled and administered [REDACTED] premedication as described above followed by treatment with AMG 330 ([REDACTED] µg/day). For these initial 3 subjects in each group, if no more than 1 DLT is observed within the DLT window, then the cohort will be expanded to enroll 6 subjects for that group. If >2 subjects have a DLT in either Arm, then, upon resolution of the AE, these subjects will be able to proceed with [REDACTED] + dexamethasone or [REDACTED] + dexamethasone as a double-agent prophylaxis. Enrollment of the remaining subjects for the Arm will be permitted, and these additional subjects will be treated with the double-agent CRS prophylaxis regimen (ie, [REDACTED] + dexamethasone in Arm 1, and [REDACTED] + dexamethasone in Arm 2).

If no more than 1 DLT is observed in the 6 evaluable subjects in either Arm, the premedication used in that Arm will be considered safe and tolerable. If [REDACTED] is determined to be safe and tolerable, Group 5 will be initiated upon DLRT recommendation, in which either [REDACTED] (as a single agent or a double-agent if combined with dexamethasone) will be further evaluated. If both

██████████ show similar CRS prophylaxis efficiency, both agents may be tested in Group 5 upon DLRM recommendation.

Subjects who receive ██████████ to administration of AMG 330 will be monitored for CRS using the guidance described in [Table 7](#). If a subject treated with AMG 330 at the 10- $\mu$ g step dose level develops grade 2 or higher CRS the subject will be able to continue the study using both ██████████ and dexamethasone or ██████████ and dexamethasone as premedication prior to the next step dose for CRS prophylaxis. This will be done in order to assess whether a double-agent regimen is more effective than single-agent for CRS prophylaxis. If AMG 330 has to be interrupted at the █████- $\mu$ g dose due to CRS and administration is restarted, the subject can receive both ██████████ and dexamethasone or ██████████ and dexamethasone as premedication.

If a subject treated with AMG 330 at the █████- $\mu$ g step dose or █████- $\mu$ g target dose level develops grade 3 or higher CRS, AMG 330 will be stopped until the severity of CRS decreases to grade 1, at which point the subject will be able to restart the cycle using either both ██████████ and dexamethasone or ██████████ and dexamethasone as premedication for CRS prophylaxis. If dexamethasone needs to be added to treat any grade CRS, the subject will continue using the double-agent prophylaxis of CRS. A maximum of 2 restarts will be allowed.

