### 3.1.6.2 Group 5 Design

Using the rules described above, if the DLRT determines that CRS incidence/severity with [REDACTED] premedication (with or without dexamethasone) is similar to or lower than that observed with dexamethasone premedication alone, then subjects with R/R AML will be enrolled into Group 5. Depending on which premedication regimen yields optimal safety results in Group 4 and based on DLRM recommendation, either [REDACTED] with or without dexamethasone will be selected for CRS prophylaxis. If a safety assessment in Group 4 shows similar results, both [REDACTED] may be tested in Group 5 in two separate cohorts. Subjects enrolled in Group 5 can continue in the study for a maximum of 6 cycles where cycles 2-6 are identical to cycle 1.

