### 3.3 Number of Subjects

Participants in this clinical investigation shall be referred to as "subjects".

It is anticipated that approximately 256 subjects will be enrolled in this study. For the dose escalation cohorts, approximately 70 subjects will be enrolled in Group 1 (R/R AML), 36 subjects will be enrolled in Group 2 (MRD+ AML) and 36 subjects will be enrolled in Group 3 (MDS). Up to 30 additional subjects will be enrolled in a dose expansion cohort for each group (up to 90 additional subjects). In addition, approximately 12 additional subjects will be enrolled in Group 4 to assess alternative CRS prophylaxis; 6 subjects for each premedication treatment arm, 6-12 subjects will be enrolled in Group 5 to assess alternative premedication in combination with mini or maxi dose steps (6 if the DLRM recommendation is to proceed with only one premedication Arm, and 12 if the recommendation is to proceed with 2 premedication Arms). For ethical and operational reasons subjects who already are in the screening phase at the time of enrollment stop (end of expansion phase) will still be allowed to be treated. Therefore, an over running of subject recruitment might be possible.

Based on emerging data, additional subjects may be enrolled.

The rationale for the number of subjects is provided in Section [10.2](#).

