**Group 5 (R/R AML):**

After the DLRM determines that ██████████ premedication is safe based on Group 4 results, then Group 5 will be initiated in subjects with R/R AML.

At completion of the dose escalation cohorts, additional subjects will be enrolled in a dose expansion cohort to gain further clinical experience, safety and efficacy data in subjects with AMG 330. The dose to be evaluated will be at or below the MTD estimated in the dose escalation cohorts.

The treatment assignment date is to be documented in the subject's medical record and on the enrollment eCRF.

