#### **10.3.1       Interim Analysis and Early Stopping Guidelines**

**Interim analyses are planned after all subjects in each indication and each phase have ended the study eg, for R/R AML: all subjects enrolled in Group 1 phase 1a, Groups 4 and 5 have ended the study. Interim analyses may be combined if the analysis timing is close or if the number of subjects in each indication or phase is small.**

Ad-hoc interim analyses for safety and preliminary efficacy updates will be performed. Data analysis prior to public disclosures (eg, scientific meetings) will also be performed. Safety data will be reviewed on an ongoing basis. Amgen, in consultation with the site investigators, will review in DLRMs all available cumulative data by indication prior to making dose escalation decisions. Adverse events and DLTs observed in all subjects will be evaluated continually by indication and fully integrated into all DLRMs and considered in all enrollment and dosing decisions.

Enrollment of a cohort can be suspended at any time based on safety findings at any dose level and in the expansion cohort, if at any time  $\geq 33\%$  of subjects treated at the MTD (including those treated at the MTD in the expansion phase) or RP2D experience a DLT within the DLT window, and a DLRM will be convened. In addition, the study may be discontinued or modified at any time due to documented safety findings.

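### Group 4: the >2-DLT switch to double-agent prophylaxis does not match the ≤1-DLT expansion and safety rules, so a count of exactly 2 triggers nothing, and after a switch the pooled count cannot judge the double agent

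*Protocol*

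**What the plan says.** Protocol 3.1.6.1.1 sets three Arm-level rules for cycle 1 of Group 4. Each Arm starts with 3 subjects on a single prophylactic agent and is planned for 6 evaluable subjects.

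- Expansion, for the first 3: "if no more than 1 DLT is observed within the DLT window, then the cohort will be expanded" to 6.
- Switch: "If >2 subjects have a DLT in either Arm, then, upon resolution of the AE", the affected subjects may go on with the agent plus dexamethasone. The Arm's remaining subjects may still be enrolled, and "these additional subjects will be treated with the double-agent CRS prophylaxis regimen".
- Safety: "If no more than 1 DLT is observed in the 6 evaluable subjects in either Arm, the premedication used in that Arm" is considered safe and tolerable. The count is for the Arm and is not split by regimen.

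The same section lets either a single or a double agent go forward to Group 5. Protocol 3.1.6.2 opens Group 5 if the DLRT finds that CRS incidence/severity with "premedication (with or without dexamethasone) is similar to or lower than that observed with dexamethasone premedication alone". Protocol 5.1 adds that this follows once the dose level review meeting determines that the "premedication is safe based on Group 4 results, then Group 5 will be initiated in subjects with R/R AML".

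The rules that act at ≥2 DLTs (Protocol 3.1.1 with Table 5, Protocol 6.2.1.4, SAP 7.1) are written for Group 1, and mTPI-2 is for Groups 2 and 3. The SAP adds no Group 4 decision rule, and its section 9.1 defers additional Group 4 and 5 analysis to a supplemental plan.

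**The concern.** Expansion and safety separate 1 DLT from 2. The switch separates 2 from 3. A count of 2 falls between them, and it is the likeliest way for the first look to fail.

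Two things are at stake. First, at 2 DLTs the written rules do not say what the Arm should do. An expanded Arm could go on assigning new subjects to a single agent that can no longer meet the safety rule. Second, a switched Arm holds at least 3 DLTs from the single agent. Its pooled result is fixed before anyone newly enrolled on the double agent is observed, although the protocol foresees taking a double agent into Group 5.

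**Working it through.** **Inputs.** 3 initial and 6 total subjects per Arm and the three thresholds, from Protocol 3.1.6.1.1. No DLT rate is given for Group 4. I assume p = 10, 20, 25 and 33%: the ends are the range in Protocol 10.2 and SAP 3.2, and 25% is the target rate in Groups 2 and 3. DLTs are taken as independent with a common p. X1 and X2 are the DLT counts in subjects 1–3 and 4–6, each Bin(3, p). An Arm with ≥2 of 3 is not expanded on the single agent.

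**Step 1: the plan's own figures.** P(at least one DLT) = 1 − (1 − p)^n. For n = 3: 1 − 0.9³ = 27.1% and 1 − 0.67³ = 69.9%. For n = 6: 1 − 0.9⁶ = 46.9% and 1 − 0.67⁶ = 91.0%. These match the stated 27–70% and 47–91%. Neither document gives operating characteristics for the Group 4 rule.

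**Step 2: what each count triggers.** Of the first 3, 0 or 1 expands, 2 has no stated action, and 3 switches. In 6 after expansion, 0 or 1 passes; 2 neither passes nor switches; 3 or more fails and meets the switch condition.

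**Step 3: probabilities per Arm.**

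| Quantity | Formula | 10% | 20% | 25% | 33% |
|---|---|---|---|---|---|
| Exactly 2 of first 3 | 3p²(1−p) | 2.7% | 9.6% | 14.1% | 21.9% |
| 3 of first 3 | p³ | 0.1% | 0.8% | 1.6% | 3.6% |
| Switch at any point | p³ + P(X1=0)P(X2=3) + P(X1=1)P(X2≥2) | 0.9% | 5.2% | 8.8% | 16.0% |
| At least one more single-agent subject after the 2nd DLT, sequential entry | P(X1=1)[1−(1−p)²] + P(X1=0)p² | 5.3% | 15.9% | 21.1% | 27.8% |

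The last row is an upper bound. It needs each DLT to be known before the next subject starts. If subjects 4–6 start together it is 0%.

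**Step 4: the pooled count after a switch.** A switch needs at least 3 DLTs in the Arm, so P(≤1 of 6) = 0 whatever the double agent's true rate. Only 3 of 3 at the first look leaves a full block of 3 to enroll on the double agent.

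**Step 5: what 3 double-agent subjects can show.** P(≤1 of 3) = (1−p)³ + 3p(1−p)², and P(≤1 of 6) = (1−p)⁶ + 6p(1−p)⁵. At 25% these are 84.4% and 53.4%; at 33%, 74.5% and 35.8%. Even 0 of 3 leaves a one-sided 95% upper bound of 1 − 0.05^(1/3) = 63%.

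**The case against.** **It may be a typing slip.** The pregnancy-test footnote reads ≥2 years in Tables 8–13 and 24 but >2 years in Tables 14–17 and 19–23, most of which are Group 4 and 5 tables. That supports a lost symbol without proving it, since ≥ survives elsewhere. If ≥2 was meant, the gap at 2 closes once the text is corrected. The pooled-count point remains.

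**There is oversight.** Protocol 10.3.2 holds review meetings for each group, with power over premedication changes, cohort expansion and dosing. Protocol 10.3.1 says "Enrollment of a cohort can be suspended at any time based on safety findings at any dose level". This stands: a 2-of-3 result has a competent decision body, and withholding expansion is itself conservative. But permission to decide is not a rule, and this section chose to write numeric ones.

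**A reader might infer that nothing governs taking the double agent to Group 5.** The documents do not support that. The CRS comparison in Protocol 3.1.6.2 covers premedication with or without dexamethasone. What is missing is narrower: a separate DLT threshold for the double agent.

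**A reader might also infer that the fallback is missed in most failing Arms.** Arms that fail ≤1 of 6 number 11.4, 34.5, 46.6 and 64.2%, and those ending at exactly 2 number 10.6, 29.3, 37.8 and 48.2%, which is 93, 85, 81 and 75% of the failures. That share overstates the consequence, for two reasons. Later paragraphs of 3.1.6.1.1 give individual subjects with CRS a route to the double agent whatever the Arm's count, although this covers treated subjects only and does not change the regimen of new ones. And 74, 67, 63 and 55% of the exactly-2 Arms reach their second DLT after expansion (for example 7.87/10.57 at 10%), where ≥2 may redirect few or no new subjects.

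**Conclusion.** Wrong as written, minor. Read literally, the switch threshold is one DLT too high for the two rules beside it. The clear effect is at the first look, where 2.7 to 21.9% of Arms have no stated action over true rates of 10 to 33%. Extra single-agent exposure after expansion lies between 0% and 5–28% of Arms, depending on how entry is staggered. Separately, the pooled ≤1-of-6 rule gives no DLT verdict on the double agent once an Arm has switched. Under the literal trigger that is uncommon, at 0.9 to 16.0% of Arms.

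These figures rest on independent DLTs at a common assumed rate. The impact is limited: Groups 4 and 5 serve an exploratory objective (Protocol 1.3), Group 4 is planned for about 12 of 256 subjects, and no MTD rule uses this branch. I draw no conclusion from the mini- and maxi-step conditions in 3.1.6.2.1 and 3.1.6.2.2, where the key words are redacted.

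**What to change.** In Protocol 3.1.6.1.1:

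- Change >2 to ≥2. Every first-look count then has an action. The first-look switch probability becomes 2.8, 10.4, 15.6 and 25.5% (exactly 2 plus 3 of 3), so the pooled-count point will matter more often and should be fixed at the same time.
- State that after a switch the single agent has failed in that Arm, including when the second DLT comes after expansion, and that DLTs in subjects enrolled on the double agent are counted separately.
- Treat a 3-subject double-agent result as preliminary for DLRT review. Do not declare safety on ≤1 of 3, which would loosen the screen as shown in step 5. Apply ≤1 of 6 only if the DLRT enrolls up to 6 on the double agent.

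The cost is one character and one or two sentences. Reaching 6 on the double agent needs at least 3 more subjects per switched Arm, which Protocol 3.3 already permits: "Based on emerging data, additional subjects may be enrolled". Tabulating DLTs and CRS by the prophylaxis in use at onset would help but is optional, because the supplemental plan may already cover it.

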- Grade 3 or 4 isolated electrolyte abnormalities (ie, those occurring without clinical consequence) that resolve, with or without intervention, to  $<$  Grade 2 levels in  $<$  72 hours will not be considered DLT.
- Grade 3 or 4 asymptomatic enzyme elevations including AST, ALT (without bilirubin elevation), GGT (gamma-glutamyl transferase), lipase and amylase that resolve to  $\leq$  Grade 2, with or without intervention, within 7 days will not be considered a DLT.
- CRS meeting any of the criteria listed below:
  - Grade 2 CRS that does not resolve, with or without intervention to Grade 1 within 7 days will be considered a DLT
  - Grade 3 CRS that does not resolve, with or without intervention to  $\leq$  Grade 2 within 5 days, or  $\leq$  grade 1 within 7 days, will be considered a DLT

- Grade 3 CRS reported at the initial dose (ie, at MTD1; applicable only after MTD1 has been defined) will be considered a DLT
- Grade 4 CRS occurring during AMG 330 treatment.
- Two separate grade 3 CRS events will be considered a DLT.

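### The Group 4 cycle 1 rules allow restart of AMG 330 after CRS of grade 3 or higher, which takes in grade 4, although the rest of the protocol requires permanent discontinuation for grade 4 CRS

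*Protocol*

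**What the plan says.** Protocol Section 3.1.6.1 refers Group 4 to the common CRS table: "If CRS occurs during treatment with AMG 330, the management guidelines in" Table 7 should be followed. Section 3.1.6.1.1 refers to Table 7 again for monitoring and then adds rules specific to Group 4 in cycle 1:

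- At the lowest named step dose, a subject who "develops grade 2 or higher CRS the subject will be able to continue the study using both" the assigned agent and dexamethasone.
- At a later step dose or the target dose, the rule applies if the subject "develops grade 3 or higher CRS, AMG 330 will be stopped until the severity of CRS decreases to grade 1". Treatment may resume after that, since the sentence goes on: "at which point the subject will be able to restart the cycle using either both". The premedication is then the assigned agent together with dexamethasone.
- "A maximum of 2 restarts will be allowed".
- At arm level: "If >2 subjects have a DLT in either Arm, then, upon resolution of the AE, these subjects will be able to proceed with" two-agent prophylaxis.

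The general rules are in Sections 6.2.1.5 and 6.6. For grade 4 CRS, the dose-delay text of 6.2.1.5 makes permanent discontinuation mandatory. The Permanent Discontinuation list in the same section has grade 4 CRS as an item of its own. The grade 4 row of Table 7 says to stop the infusion and discontinue for good. The restart procedure in 6.6 is headed for CRS interruptions generally, but its criteria are written for grade 3.

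**The concern.** Grade 4 CRS in Table 7 means life-threatening symptoms: ventilator support, or grade 4 organ toxicity other than transaminitis. A Group 4 rule that lets such a subject restart once symptoms fall to grade 1 permits re-exposure that the rest of the protocol forbids. It does so where dexamethasone, the standard prophylaxis, is withheld at the start of cycle 1. A site that treats the Group 4 text as the specific rule, overriding the general one, would reach the unsafe answer. What is at stake is the safety of individual subjects, not the statistical operating characteristics.

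**Working it through.** The plan states no figure to reproduce. The check is a comparison of texts, plus a count of the subjects covered.

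**Step 1: what the wording includes.** Table 7 grades CRS from 1 to 4. The Group 4 sentence starts at grade 3 and sets no upper limit, so the part above grade 3 can only be grade 4. Redactions in that paragraph hide doses and agent names, not grades.

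**Step 2: the rules side by side** (Group 4, cycle 1, step or target dose covered by the sentence).

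| Event | Section 3.1.6.1.1 | Sections 6.2.1.5 and 6.6 with Table 7 | Result |
|---|---|---|---|
| One grade 3 event, resolving in time | Stop; restart at grade 1 with two agents | Interrupt; restart at grade 1 or less after consulting the medical monitor | Compatible |
| Grade 3, slow to resolve | Stop until grade 1; no time limit | Permanent discontinuation if not grade 2 or less within 5 days, or grade 1 or less within 7 days | Group 4 text silent |
| Second separate grade 3 event | Ceiling of 2 restarts | Permanent discontinuation | Group 4 text silent |
| Grade 4 | Stop; restart at grade 1 with two agents | Permanent discontinuation | Conflict |

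Only the last row is a contradiction. One rule permits what three other places forbid. In the two middle rows the Group 4 text simply does not repeat a limit set elsewhere.

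**Step 3: is there an exemption?** Section 6.2.1.5 allows restart after a DLT in a subject with clear clinical benefit, but that exception is attached to the DLT item. The grade 4 CRS item has none. The Group 4 and 5 exception in Section 6.3 concerns dexamethasone use. I found no statement that Group 4 is exempt from the CRS discontinuation rules, and none that says which section prevails.

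**Step 4: subjects covered.** Section 3.3 says "approximately 12 additional subjects will be enrolled in Group 4 to assess alternative CRS prophylaxis", 6 per arm: 2 × 6 = 12.

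**Step 5: restarts permitted after grade 4 CRS.** Under 3.1.6.1.1, at least 1, with a ceiling of 2. Under 6.2.1.5 and Table 7, 0.

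**Step 6: effect on decisions.** Section 6.2.1.4 lists as a DLT "Grade 4 CRS occurring during AMG 330 treatment". The event counts as a DLT whether or not the subject restarts, so the arm-level count and the criteria for opening Group 5 do not change.

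**The case against.** The strongest reply is that the safe rule already governs Group 4. The parent section and the paragraph itself both refer to Table 7, and Section 6.2.1.5 applies to all groups. The Group 4 sentence is permissive and the others are mandatory, so an investigator who discontinues at grade 4 breaches nothing. On this view the paragraph is about which premedication goes with a restart, not which grades may be rechallenged.

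Much of that stands. It makes the misreading less likely, and it would be wrong to say that no course of action satisfies both texts, because discontinuing does. It does not answer the point that a current, specific Group 4 rule permits re-exposure after grade 4 CRS, with no exclusion and no order of precedence.

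The objection also succeeds against three wider readings that a reader might draw:

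- *The ceiling of two restarts contradicts the rule on two grade 3 events.* A ceiling promises no restart, and it can cover interruptions for other reasons.
- *The sentence starting at grade 2 authorises continuation after grade 4.* It says when a second agent may be added before the next step. It has no upper limit and should be tidied, but the actions for grades 3 and 4 remain in Table 7.
- *The provision for subjects with a DLT should be placed under the whole of Section 6.2.1.5.* That list opens with dose-limiting toxicity, excepted only where there is clear clinical benefit. Subordination would largely cancel a planned continuation on two agents, and assessing two-agent prophylaxis is a stated purpose in this section. That would be a design change.

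**Conclusion.** The contradiction is real and limited to grade 4 CRS at the step and target doses named in Section 3.1.6.1.1. It bears on about 12 subjects and permits one or two restarts where the general rules permit none. It should be corrected because the event is life-threatening and the text is plain.

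The documents do not support a statement of how often this would arise. A reader might compute 1 − (1 − p)^12 with assumed per-subject grade 4 rates of 1%, 5% and 10%, giving 11%, 46% and 72%. Those rates are assumptions. The formula also counts all 12 subjects at any dose, whereas the rule covers only certain dose levels, which some subjects may not reach. Even then it would give the chance of meeting the conflicting rules, not of re-exposure. Nor do the documents support an inference that the sponsor intends to rechallenge after grade 4, given the references to Table 7, or that dose decisions are biased. The conclusion rests on the wording alone and needs no assumed rate.

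**What to change.** In the restart paragraph of Section 3.1.6.1.1:

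1. Replace *grade 3 or higher CRS* with *grade 3 CRS*.
2. Add that grade 4 CRS requires permanent discontinuation under Section 6.2.1.5 and Table 7.
3. Add that restart and continuation under this paragraph remain subject to the CRS-specific discontinuation criteria: grade 4 CRS, two separate grade 3 events, and the 5-day and 7-day limits on resolution. This also closes the open upper end of the sentence starting at grade 2, and the silence on the second grade 3 event.

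Leave the provision for subjects with a DLT as it is, or at most add that subjects with grade 4 CRS may not proceed under it.

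The cost is a few words and two sentences in the next amendment. Sample size, DLT definition, decision rules and analysis stay as they are.
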